## **RESULTS**

### *Participant Characteristics*

Screening, recruitment and follow-up of subjects occurred between August 2012 to October 2018, and data was locked May 2019. Recruitment ended to allow for clinical outcome analysis. *From the 688 infants assessed for eligibility, ARI was: normal (<3%) in 246 (36%), indeterminate (3-7%) in 169 (25%), and abnormal (>7%) in 273 (40%). Study enrollment, randomization, and primary outcome analysis are described in the CONSORT diagram (Fig 1). Demographic and clinical characteristics at allocation were not significantly different in both groups (Table 1).* Frequency (%) of GERD referral reasons were for respiratory concerns (apnea/bradycardia/desaturation, airway management, or suspected aspiration) in 54%, feeding concerns (poor oral feeding or intolerance) in 47%, and GERD type symptoms (arching/irritability or emesis) in 25% (note proportions do not add to 100 due to providers being able to list multiple reasons for referral). Reasons for referral did not differ between conventional and study groups (all  $P>0.05$ ). Proportion of milk types (exclusive breast milk: exclusive formula: combination of formula and breast milk, %) were not different between groups: 19: 67: 14 in conventional vs 18: 53: 3 in study groups ( $P=0.24$ ). Of those formula fed (28 in conventional group, and 29 in study group) proportion of formula types (hydrolyzed: gentle: low lactose: preterm: standard, %) were: 4:7:4:75:10 in conventional vs 10:10:0:69:10 in study groups ( $P=0.84$ ). Caloric density ranged

from 19 cal/oz to 30 cal/oz, and the proportions (%) (19: 20: 22: 24: 27: 30 cal/oz) for conventional (11: 31: 33: 19: 6) and study groups (8: 20: 30: 35: 3) did not differ ( $P = 0.47$ ). Breast milk intake in both groups was 40% at inception ( $P=1.0$ ), and the caloric density (cal/oz) for the conventional vs. study groups was 24 [22-25] and 24 [22-27] respectively ( $P=0.41$ ) For conventional and study groups respectively, acid suppressive dose (mg/kg/dose BID) was 0.75 [0.75 – 0.75] vs 0.75 [0.75 – 0.75],  $p=0.27$  upon initial dose, and 0.75 [0.75 – 1.0] vs 1.0 [0.75 – 1.0],  $p=0.09$  at follow-up.

## STUDY OUTCOMES

### Primary and Secondary Clinical Outcomes

The clinically meaningful primary and secondary outcomes did not differ significantly between groups (**Table 2**). I-GERQ-R scores for study and conventional groups are shown (**Fig 2**). At inception: positive I-GERQ-R was 19/35 (54%) in the conventional group vs 24/37 (65%) in the study group,  $p=0.36$ . At Time-2: positive I-GERQ-R prevalence was 9/31 (29%) in the conventional group vs 13/34 (38%) in the study group,  $p=0.43$ . In the study group vs conventional group, respectively: a) primary outcome achieved in 33% (95% CI, 19% - 49%) vs 44% (95% CI, 28% - 62%) ( $p=0.28$ ), b) secondary outcomes: independent oral feeding in 65% (95% CI, 48% - 80%) vs 77% (95% CI, 60% - 90%),  $p=0.26$ ,  $\geq 6$ -point I-GERQ-R decrease in 38% (95% CI, 22% - 56%) vs 35% (95% CI, 19% - 55%),  $p=0.82$ , length of stay was 98 [81-132] days vs 108 [83-125] days,  $p=0.89$ , and oxygen requirement at discharge in 19% (95% CI, 8% - 35%) vs 26% (95% CI, 13% - 43%),  $p=0.49$ . There were no significant differences in growth metrics (all  $p>0.05$ ) or developmental scores at 2 years (all  $p>0.05$ ). Feeding outcomes or I-GERQ-R scores did not significantly differ between conventional vs study groups based on feeding method at inception (**Table 3**). Individual I-GERQ-R questions relating to vomiting, regurgitation, and crying (i.e. frequency of emesis, volume of emesis, symptoms with emesis, and crying more than usual in the

past week) had no differences ( $P>0.05$ ) within the group or between the groups across maturation for these individual symptoms, except for symptoms with emesis (never: rarely: sometimes: often: always, %) was 16:16:42:19:6 for conventional group at Time-1 vs 18:18:29:0:35 for study group at Time-1,  $p < 0.01$ .

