## OUTCOME MEASURES

The *a priori primary end-point* was achieving independent oral feeds and/or a six-point decrease in I-GERQ-R score at 5 weeks or sooner, whichever was earliest at discharge. *To clarify further, there were 2 scenarios:* 1) Among infants who were transitioning to oral feeds (gavage fed) at inception: success was defined as achieving full oral feeds or a  $\geq 6$ -point decrease from baseline I-GERQ-R. 2) Among infants who were on full oral feeds at inception, success was determined if full oral feeds were maintained plus a  $\geq 6$ -points decrease from baseline I-GERQ-R. *Secondary end-points* included growth metrics (weight, length and head circumference), supplemental oxygen, economic metrics (LOHS), long-term feeding outcomes at 6 months and 1 year, and developmental outcomes at 2 years (32, 33).

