## STATISTICAL METHODS

Based on our preliminary data, we had planned to enroll 100 patients (50 per group) to detect 27% or higher increase in proportion of success of study group compared to the conventional group with 80% power and overall one-sided  $\alpha$  level of 0.025. One interim futility analysis was planned at about 50% information prior to the final analysis at 100% information, corresponding to 50 and 100 evaluable patients, respectively. The boundary was determined using Lan-DeMets spending functions to simulate O'Brein-Fleming boundaries(34). Using the target proportion of success, the boundary at the futility analysis was  $p>0.297$ .

Seventy-six infants were randomly assigned till the end of funding for this study and were included in the analysis of demographics and clinical characteristics (**Fig 1, Table 1**) and primary outcome by intent-to-treat. If a patient dropped out before the end of study and no symptom score was evaluable, we treated the patient as a failure for the primary outcome by intention-to-treat. Secondary outcome analysis was performed for 72 subjects (**Fig 1**). Futility boundary was not reached at interim analysis of 50 patients ( $p=0.1 < 0.297$ ) and accrual was continued with DSMB approval. Summary statistics were calculated for patient demographics and clinical characteristics for final analysis. Success rate in achieving PO or reduction in the I-GERQ-R by 6-points was calculated with 95% confidence interval and compared using chi-square test between the conventional and study groups (primary outcomes) for the intention-to-treat and treat-as-treated analyses. Fisher's exact or chi-square test were used to compare other categorical secondary outcomes including feeding method and supplemental oxygen between the groups. Shapiro-Wilk test for normality was used for the continuous outcomes. Paired t-tests or Wilcoxon singed-rank

tests were used to assess changes in growth velocity and feeding therapy characteristics between time-1 and time-2. Two sample t-tests or Wilcoxon rank-sum tests were used to compare these continuous outcomes between conventional and study groups. Median (interquartile range [IQR]), mean (SD), or % was reported, unless stated otherwise.  $P$  values  $<0.05$  were considered statistically significant, and SAS version 9.4 (SAS, Inc, an IBM Company, Chicago, IL) was used.

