**Table 1. Baseline Demographic and Clinical Characteristics of Enrolled Participants**

Variable	Overall Subjects (N = 76)	Conventional Group (N = 36)	Study Group (N = 40)
At Birth			
Gender, Female – n (%)	37 (49)	18 (50)	19 (48)
Race – n (%)			
African American	11 (15)	3 (8)	8 (20)
Asian	1 (1)	0 (0)	1 (3)
Other	6 (8)	2 (6)	4 (10)
Unknown	1 (1)	1 (3)	0 (0)
White	57 (75)	30 (83)	27 (68)
Ethnicity – n (%)			
Hispanic or Latino	2 (3)	2 (6)	0 (0)
Non Hispanic or Latino	71 (93)	32 (89)	39 (98)
Unknown	3 (4)	2 (6)	1 (3)
Gestational Age (GA) – wks	29.3 [27 - 32.9]	29.3 [28 - 32.2]	29.2 [27 - 33.1]
Preterm birth – n (%)	68 (90)	34 (94)	34 (85)
Birth Weight – kg	1.23 [0.9 - 1.9]	1.2 [0.9 - 1.9]	1.3 [0.9 - 2.1]
Size for Gestational Age – n (%)			
Small (< 10th %)	9 (12)	5 (14)	4 (10)
Average (10th - 90th %)	58 (76)	26 (72)	32 (80)
Large (> 90th %)	9 (12)	5 (14)	4 (10)
Cesarean Delivery – n (%)	50 (66)	22 (61)	28 (70)
At Inception			
Postmenstrual age – wks	41.1 (2.5)	41.3 (2.2)	40.9 (2.7)
Chronologic age – wks	10.9 (4.3)	11.1 (4.5)	10.7 (4.3)
Weight – kg	3.5 (0.8)	3.5 (0.8)	3.5 (0.8)
O 2 Requirement at 36 wks PMA – n (%)	36 (47)	17 (47)	19 (48)
O 2 Requirement at 28 days age – n (%)	46 (61)	21 (58)	25 (63)
Feeding Method – n (%)			
Gavage	2 (3)	0 (0)	2 (5)
Transitional	37 (49)	18 (50)	19 (48)
Oral	37 (49)	18 (50)	19 (48)
Nasal Cannula Oxygen – n (%)	23 (30)	11 (31)	12 (30)
Total Intake Volume – mL/kg/day	150 [149 - 154]	150 [148 - 152]	150 [150 - 157]
Total Oral Intake Volume – mL/kg/day	112 [45 - 150]	112 [57 - 150]	112 [22 - 148]
Acid Reflux Index (ARI) – %	9.3 [6.0 - 17.1]	10 [6.0 - 16.7]	9.1 [5.0 - 17.6]
ARI Category – n (%)			
Indeterminate (ARI 3 - 7%)	26 (34)	12 (33)	14 (35)
Abnormal (ARI > 7%)	50 (66)	24 (67)	26 (65)

Data presented as n (%), Median [IQR], or Mean (SD).

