### 3.3 Statistical procedures

- Statistical Analyses:
  - Aim I: Outcomes: We will test the hypothesis that the innovative feeding strategy provided over 4 wks is more effective than standard therapy for the acquisition of safe feeding skills by improved symptom scores (Primary), improved individual I-GERQ-R measures, growth measures, reduced lengths of stay and resource utilization (Secondary). Linear mixed models will be used to study the associations between the primary endpoints for Aim 1 (symptom scores) and treatment, and trend across time. The interaction term “group x time” will be included in the model to study whether the two treatment groups have different “behavior” across time. Confounder variables, such as medications, feeding position or volume, will be included in the models. Logistic regression models will be used to assess success of the treatment vs. standard of care. Also, potential confounders (e.g. feeding method: oral vs. tube) will be included and studied in these models. Holm’s method will be used to adjust for multiple comparisons (150). All the secondary variables listed above, will be analyzed using either linear mixed models or logistic regression models. Model goodness of fit tests and residual analyses will be performed to assess the models. Interaction terms and potential confounder variables will be included.
  - Aim II: Mechanistic Hypothesis: We will test the hypothesis that the sensory-motor characteristics of aerodigestive reflexes evoked with induced esophageal stimulation or upon spontaneous esophageal provocation as in GER, improve in the innovative therapy group with regards to: sensory thresholds, response latency and duration, frequency and magnitude of reflexes, TLESRs, spatial-temporal-physical- chemical characteristics of GER events with associated symptom indices. Based on the preliminary data, we will have at least 80% power to detect the above differences of pre and post therapy between the two groups. Linear mixed models or logistic regression models (depending on the nature of the outcome variable) will be used to study the associations of interest within sensory motor components of aerodigestive reflexes within and between study groups and their outcomes. Potential confounders as well as interaction between groups and type of infusion will be included in the models. We have utilized similar models previously. Correlation between symptom indices (SI, SSI, SAP) and reflexes will be calculated.

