## 4.0 Study Endpoints

- Primary Outcome
  - **Clinical outcome of feeding success for those infants transitioning to oral feeds at inception.**
    - The primary endpoint is the feeding success defined as achieving full oral feeds (defined as no need for tube feeds to maintain hydration and nutrition) and/or a  $>/=$  6-point decrease from baseline I-GERQ-R. The time frame is up to 5 weeks after enrollment.
  - **Clinical outcome of feeding success for those infants on full oral feeds at inception.**
    - The primary endpoint is the feeding success defined as maintaining full oral feeds and a  $>/=$  6-point decrease from baseline I-GERQ-R. The time frame is up to 5 weeks after enrollment.
- Secondary Outcomes
  - Clinical Outcomes
    - Length of hospital stay
    - Growth outcomes during the study period and up to 1 year
    - Independent feeding skills over time up to 1 year
    - Respiratory support during the study period and at discharge
    - Developmental outcomes with Bayley's scores at 2 years
    - Individual differences in I-GERQ-R questionnaire
  - Motility Outcomes
    - Mechanisms of aerodigestive clearance and esophageal provocation are evaluated based on esophageal motility studies at inception and after 5 weeks.
  - pH Impedance outcomes
    - 24-hour pH impedance results at inception of study and then 5 weeks later after treatment completed

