## **6.0 Procedures Involved\***

### **6.1 Study design:**

- Study design and setting: This is a Single Center Prospective Randomized, Blinded Controlled Trial. Consented subjects will undergo 1:1 randomization into either innovative feeding strategy and standard therapy arms.
- Patient Population: Potential study subjects are those that are referred by their attending physician for evaluation and management of potential GERD, the key symptoms being irritability and arching, gagging, choking, coughing, aspiration, life threatening events, swallowing problems, and/or failure to thrive. I-GERQ-R questionnaire will be completed as per guidelines. Each patient must have a signed consent from parent/legal guardian prior to initiation of screening for the trial.
- Inclusion Criteria: Hospitalized convalescing infants with aerodigestive symptoms or admitted for GERD symptoms, < 42 weeks GA. Infants will be included if PMA at time of study is  $\geq$  34 wks age and  $\leq$  60 wks. Subjects must be on full enteral feeds defined as  $\geq$  150mL/k/day. Infants must be breathing unaided, and nasal cannula oxygen up to 1 LPM is allowed. In subjects receiving empiric prokinetics or acid suppressive agents, the medications need to be stopped for  $\geq$  72 hr prior to evaluation.
- Exclusion Criteria: Infants with known genetic, metabolic or syndromic disease, neurological diseases such as Grade III or IV intra ventricular hemorrhage or perinatal asphyxia, GI malformations and surgical GI conditions.
- Tests and procedures
  - Twenty-four-hour pH and impedance ordered diagnostically for suspected GERD
  - If RI  $>3$  and infant meets all above criteria, infant randomized into conventional or study group
  - Esophageal manometry performed
  - 4 weeks of the study intervention for the study group and standard treatment for the conventional group while collecting data on symptoms, feeding position, duration and volume

- Omeprazole stopped after 4-week course.
- Repeat esophageal manometry and pH impedance testing done after 1 week off omeprazole (at week 5). If the providers/parents are resistant or refuse to stop the medication, repeat testing will still be done, and the alteration will be noted.

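### For infants already on full oral feeds, success turns on a 6-point I-GERQ-R fall, yet baseline I-GERQ-R is in neither the primary test nor the named covariates

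*Combined protocol and SAP*

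**What the plan says.** - **Endpoint.** The report's Outcome Measures section has two rules. For infants still moving to oral feeding, "success was defined as achieving full oral feeds or a" fall of 6 points or more. For infants already on full oral feeds, "success was determined if full oral feeds were maintained plus a" fall of that size. Protocol section 4.0 makes the same split, with the fall being at least a "6-point decrease from baseline I-GERQ-R".
- **Entry.** Section 6.1 says the "I-GERQ-R questionnaire will be completed as per guidelines". Neither that section, section 9.0 nor the report's participant selection section sets a minimum score. Randomisation is stratified by acid reflux index and birth gestation only.
- **Analysis.** In Statistical Methods the primary success rates are "compared using chi-square test between the conventional and study groups". Protocol section 3.3 also plans logistic regression for success, in which "potential confounders (e.g. feeding method: oral vs. tube) will be included", and a linear mixed model for symptom scores with a group-by-time term. Baseline I-GERQ-R is not named as a covariate for success.
- **Data.** The outcomes section says that at inception "positive I-GERQ-R was 19/35 (54%) in the conventional group" against 24/37 (65%) in the study group, p=0.36. Table 1 has no I-GERQ-R row.

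**The concern.** An infant with a low starting score has little room to fall 6 points, and one with a high score tends to fall through regression to the mean alone. Baseline score should therefore be a strong predictor of the fall, and through it of success in the orally fed half of the trial. It was collected on the same form as the outcome. Leaving it out wastes information in a trial that randomised 76 infants against a target of 100 evaluable. It also leaves the estimate, and the 6-point component in particular, exposed to whatever baseline difference chance produced.

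**Working it through.** **1. Reported figures.** Pearson chi-square without continuity correction reproduces all three:
- baseline 19/35 v 24/37: p=0.360 (stated 0.36)
- primary 16/36 v 13/40: p=0.284 (stated 0.28)
- 6-point fall 11/31 v 13/34: p=0.818 (stated 0.82)

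**2. Who depends on the fall.**
- Orally fed at inception (Table 1): 18 + 19 = 37 of 76 (49%). In Table 3, 16/17 and 17/17 kept full oral feeding. Success there was 4/14 and 5/14, the same counts as for the fall alone.
- Tube fed at inception (Table 3, with the N line taken as separate from the outcome rows): oral feeding 11 and 7, fall 7 and 8, either 14 and 13, both 4 and 2. The reading is consistent: 11+7-4=14 and 7+8-2=13. Successes without a fall are 14-7=7 and 13-8=5, so 12 of 27.
- Negative at baseline: (35-19)+(37-24) = 29 of 72 (40%).

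**3. Effect of the baseline difference, from the reported counts.** The documents do not give success by baseline score, so only a range is possible. The imbalance is 64.9-54.3 = 10.6 points (95% CI -12.0 to +33.1). The shift in the arm difference is 10.6 points times the gap in success rate between positive and negative infants: a 20-point gap gives 2.1, 40 gives 4.2 and 60 gives 6.3.
- Extreme for orally fed infants (no negative infant succeeds): success among positives = (9/28)/(43/72) = 53.8%. The shift is 0.538 x 10.6 = 5.7 points in that group and 5.7 x 37/76 = 2.8 overall.
- Extreme for the whole endpoint: (29/76)/(43/72) = 63.9%, shift 6.8 points.
- Observed difference, study minus conventional: 32.5-44.4 = -11.9 points (95% CI -33.7 to +9.8). Removing these shifts gives -14.7 or -18.7 (approximate CI for the latter -40.5 to +3.1).
- Mantel-Haenszel over the 72 classified infants, with all 29 successes placed among them: -10.6 unadjusted. It becomes -11.1 to -17.9 for every split in which positives do at least as well as negatives in both arms.

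Table 3 adds to 14+4=18 and 13+5=18 successes, against 16 and 13 in Table 2. That is a separate matter to reconcile, but it limits how finely these figures can be read.

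**4. Effect under an assumed score distribution.** Assumptions not in the documents: SD 6, mean fall 3.5, correlation r between baseline and follow-up from 0.3 to 0.7.
- 54% v 65% positive corresponds to 6 x [z(0.649) - z(0.543)] = 6 x 0.274 = 1.64, so about 1.7 points.
- SD of the fall = 6√(2(1-r)). P(fall ≥6) = Φ((3.5-6)/SD), and with a 1.7-point higher baseline Φ((3.5+1.7(1-r)-6)/SD).
- r=0.3: SD 7.10, 36.2% to 42.7%, shift 6.4 points. r=0.7: SD 4.65, 29.5% to 33.4%, shift 3.9 points.
- By baseline quartile, the fall occurs in about 10-14% of the lowest and 48-68% of the highest.
- Composite: orally fed infants carry the full shift, and tube-fed infants only where oral feeding was not reached (18/38 reached it; assumed independent of score). The factor is 37/76 + (39/76)(20/38) = 0.757, so the shift is 0.757 x 3.9 = 3.0 to 0.757 x 6.4 = 4.9 points.

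**5. Power on the composite.** Simulation with 50 per arm and feeding method already in the model. Further assumptions: a 3.5-point treatment effect on the score, and 45% v 65% reaching oral feeds. Adding baseline raises power from 55% to 61% (r=0.3), 64% to 70% (r=0.5) and 81% to 82% (r=0.7). Across the runs and settings tried, the gain was roughly 1 to 7 points.

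**The case against.** The strongest reply is that the unadjusted test is valid under randomisation and that the protocol largely covers the point. Its list of confounders is introduced as an example, so it is open, and the mixed model of symptom scores uses baseline and follow-up values. This stands in part. But an open list does not commit anyone to the baseline score, and the mixed model analyses the score rather than the binary primary outcome.

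A reader might also infer three stronger things that the documents do not support.

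- *That success in general requires the fall, so low scorers can hardly succeed.* Infants moving to oral feeds can succeed by oral feeding alone, and 12 of the 27 tube-fed successes in Table 3 did.
- *That the baseline imbalance biases the comparison or explains the null result.* A 10.6-point difference with p=0.36 is compatible with chance. It would favour the study arm, which had the lower success rate. The one questionnaire item reported to differ at inception (symptoms with emesis always present, 6% conventional v 35% study) points the same way.
- *That infants scoring below 6 cannot succeed and should be set aside in a sensitivity analysis.* This needs a scale minimum of 0, which is not stated, and the number of such infants is not given. Nor is the cutoff for a positive score, so the 29 negative infants cannot be equated with infants blocked by a floor.

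**Conclusion.** The point holds as a modest loss of precision. For about half the infants the primary outcome is in effect the 6-point fall, and its most obvious predictor, already collected, is in neither the reported test nor the named covariates. The unadjusted comparison remains valid. If baseline-positive infants do at least as well as negative ones, adjustment moves the difference further below -11.9 points, so the finding of no superiority does not change. A reader should not expect adjustment to rescue the bundle.

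The 3-to-5-point composite shift and the 1-to-7-point power gain rest on the assumed SD, mean fall and correlation, and the power gain also on an assumed treatment effect. The score distributions are in Figure 2, which was not available, so these assumptions could not be checked. The 6-point component is the most sensitive: 13/34 v 11/31 differ by 2.8 points, less than the 4 to 6 points that the baseline difference could contribute under these assumptions, so its sign could reverse.

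**What to change.** In the planned logistic model for the primary outcome, and in the same model for the 6-point component, name continuous baseline I-GERQ-R and feeding method at inception as covariates. Report a risk difference standardised over both arms, with its confidence interval, beside the unadjusted one. State how an infant without a baseline score is handled, because positivity at inception is reported for 72 of the 76. Add baseline I-GERQ-R by arm to Table 1, and show success by baseline score. Eligibility and the endpoint stay as they are. Since the results are known, label the adjusted estimate as supplementary. The cost is a few lines of SAP wording and one re-run on data already held.

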## **ABSTRACT**

**OBJECTIVE:** To test the hypothesis that a feeding-bundle concurrent with acid-suppression is superior to acid-suppression alone in improving gastroesophageal reflux disease (GERD) attributed-symptom scores and feeding outcomes in neonatal ICU infants.

**METHODS:** Infants (N=76) between 34-60 weeks' postmenstrual age with acid reflux index>3% were randomly allocated to study (acid suppressive therapy + feeding bundle) or conventional (acid suppressive therapy only) arms for 4 weeks. Feeding bundle included: total fluid volume <140 ml/kg/day, fed over 30 min in right lateral position, and supine postprandial position. Primary outcome was independent oral feeding and/or  $\geq 6$ -point decrease in symptom score (I-GERQ-R). Secondary outcomes included growth (weight, length, head circumference), length of hospital stay (LOHS, days), airway (oxygen at discharge), and developmental (Bayley scores) milestones.

**RESULTS:** Of 688 screened: 76 infants were randomized and used for the primary outcome as intent-to-treat, and secondary outcomes analyzed for 72 infants (N=35 conventional, N=37 study). For study vs conventional groups, respectively: a) 33%(95% CI, 19%-49%) vs 44%(95% CI, 28%-62%), p=0.28 achieved primary outcome success, and b) secondary outcomes did not significantly differ (p>0.05).

**CONCLUSIONS:** Feeding strategy modifications concurrent with acid suppression are not superior to PPI alone in improving GERD symptoms or discharge feeding, short-term and long-term outcomes.

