**Table 2. Primary and Secondary Clinical Outcomes and Compliance Measures**

Primary Outcome (intent-to-treat analysis)	Overall (N = 76)	Conventional (N = 36)	Study (N = 40)	P-value
A priori clinical outcome Success, n (%)	29 (38)	16 (44)	13 (33)	0.28
Secondary Outcomes	Overall (N = 72)	Conventional (N = 35)	Study (N = 37)	P-value
I-GERQ-R decrease by 6 – n (%)	24/65 (37)	11/31 (35)	13/34 (38)	0.82
Feeding Outcome at Time 2 – n (%)				0.26
PO	51 (71)	27 (77)	24 (65)	
Transition (PO + Tube)	18 (25)	8 (23)	10 (27)	
Tube	3 (4)	0 (0)	3 (8)	
Length of hospital stay – days	108 [82 - 128]	108 [83 - 125]	98 [81 - 132]	0.89
Hospital stay Inception to Discharge – days	25 [11 - 45]	23 [3 - 39]	27 [16 - 47]	0.26
Weight Growth Velocity (GV) – g/day	27.1 (9.4)	26.5 (7.2)	27.6 (11.1)	0.64
Length GV – cm/day*	0.1 (0.1)	0.1 (0.1)	0.1 (0.1)	0.88
Head Circumference GV – cm/day*	0.1 [0.0 - 0.1]	0.1 [0.0 - 0.1]	0.1 [0.0 - 0.1]	0.87
Feeding Method at Discharge – n (%)				0.32
PO	54 (75)	29 (83)	25 (68)	
Transition (PO + Tube)	14 (19)	5 (14)	9 (24)	
Tube	4 (6)	1 (3)	3 (8)	
Oxygen Requirement at discharge – n (%)	16 (22)	9 (26)	7 (19)	0.49
Compliance to Feeding Methods				
Total Fluid Volume (TFV)				
TFV at Inception- #	N/A	150 [147, 152]	150 [149, 156]	0.8
TFV at Time 2- #	N/A	143 [134, 148]*	133 [126, 137]*	<0.001
# days TFV ≤ 140 / kg / day	N/A	10 [2, 26]	22 [11, 31]	0.005
TFV compliance (TFV <140/kg/d for >75% of time)	N/A	9 (26)	27 (73)	<0.001
Position				
Feeding Position, RSL, %	N/A	5 [1, 17]	78 [12, 94]	<0.001
Feeding in RSL >75% of the time, %	N/A	0 (0)	21 (57)	<0.001
Supine Position Post-Prandial, %	N/A	50 [40, 66]	87 [74, 96]	<0.001
Supine Position Post-prandial >75% of the time, %	N/A	7/34 (21)	27/36 (75)	<0.001
Feeding Duration				
% time feed duration >30 min, %	N/A	4 [0, 37]	15 [0, 69]	0.15
Feeding Duration at Inception, min	N/A	23 [17, 41]	30 [19, 34]	0.64
Feeding Duration at Time 2, min	N/A	23 [18, 28]	26 [20, 30]	0.15
Long-term Follow-up†				
Feeding Method at 6 months – n (%)				0.65
PO	36/50 (72)	21/27 (78)	15/23 (65)	
Transition (PO + Tube)	10/50 (20)	4/27 (15)	6/23 (26)	
Tube	4/50 (8)	2/27 (7)	2/23 (9)	
Feeding Method at 1 year – n (%)				0.11
PO	37/44 (84)	20/22 (91)	17/22 (77)	
Transition (PO + Tube)	4/44 (9)	0/22 (0)	4/22 (18)	
Tube	3/44 (7)	2/22 (9)	1/22 (5)	
CCABSID-III				
Cognitive Score <80 – n (%)	9/44 (21)	5/23 (22)	4/21 (19)	1.00
Cognitive Score – #	95 [90 - 105]	100 [90 - 105]	90 [90 - 100]	0.11

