**Table 3. Feeding and I-GERQ-R Outcomes by Feeding Method at Inception**

Outcome	Conventional	Study	P-value
Among those Tube fed at Inception			
Achieved exclusive oral feeding	N = 18	N = 20	
Achieved I-GERQ-R decrease $\geq 6$	11 (61)	7 (35)	0.11
Achieved PO or I-GERQ-R decrease $\geq 6$	7/17 (41)	8 (40)	0.94
Achieved exclusive oral feeding + I-GERQ-R decrease $\geq 6$	14 (78)	13 (65)	0.39
	4/17 (24)	2 (10)	0.38
Among those PO fed at Inception	N = 17	N = 17	
Maintained PO	16 (94)	17 (100)	1.0
Achieved I-GERQ-R decrease $\geq 6$	4/14 (29)	5/14 (36)	1.0
Maintained PO or I-GERQ-R decrease $\geq 6$	16 (94)	17 (100)	1.0
Maintained PO + I-GERQ-R decrease $\geq 6$	4/14 (29)	5/14 (36)	1.0

[figure not shown]
Data presented as n (%).

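### The reported primary successes (16/36 conventional, 13/40 study) do not reconcile with Table 3, which gives 18 and 18 under the stated rule at Time 2

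*Combined protocol and SAP*

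**What the plan says.** The Abstract reports "33%(95% CI, 19%-49%) vs 44%(95% CI, 28%-62%), p=0.28 achieved primary outcome success", study arm first. The Results section on primary and secondary outcomes repeats it: "primary outcome achieved in 33% (95% CI, 19% - 49%) vs 44% (95% CI, 28% - 62"%). Table 2, in the row "clinical outcome Success, n", gives the counts by intention to treat: 16 of 36 conventional, 13 of 40 study, 29 of 76 overall.

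The definition has two branches, the same in Outcome Measures and in protocol Section 4.0. An infant still moving to oral feeds at inception succeeds by reaching full oral feeds or by a fall of at least 6 points on the I-GERQ-R. For an infant already on full oral feeds, "success was determined if full oral feeds were maintained plus a" fall of the same size.

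Table 3 splits outcomes by feeding method at inception and contains both branches: "Achieved PO or I-GERQ-R decrease" of at least 6 for the tube-fed, and "Maintained PO + I-GERQ-R decrease" of at least 6 for the orally fed.

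Statistical Methods and the intention-to-treat part of Section 3.3 count an infant as a failure if the infant drops out and has no symptom score. On timing, Section 6.1 uses Time 2, or discharge where Time 2 was not completed. Outcome Measures sets 5 weeks or discharge, whichever comes earlier.

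**The concern.** A reader who applies the published definition to the published Table 3 gets 36 successes in total, not 29, and equal numbers in the two arms. The figure affected is the trial's primary estimate, with its interval and p-value, and it appears in the Abstract, the Results and Table 2.

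The decision on superiority is not at stake. What is at stake is the size of the apparent deficit in the study arm and the largest benefit the data leave open. Both bear on the firm wording in the Key Points and Conclusion that the feeding strategy has no impact or role. As the text stands, the reader also cannot tell which assessment time or failure rule produced the headline.

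**Working it through.** **1. The reported figures follow from 16 and 13.** Exact (Clopper-Pearson) intervals: 16/36 = 44.4% (27.9 to 61.9); 13/40 = 32.5% (18.6 to 49.1). Uncorrected chi-square p = 0.2845. These match the printed 28-62, 19-49 and 0.28, so the counts are not a misprint in one place.

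**2. Reading Table 3.** In the text read here, the labels of the tube-fed block sit one line above their values (an extraction effect). The intended alignment is:

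| Inception feeding | Criterion | Conventional | Study |
|---|---|---|---|
| Tube-fed | Full oral feeds | 11/18 | 7/20 |
| Tube-fed | Fall ≥6 | 7/17 | 8/20 |
| Tube-fed | Either | 14/18 | 13/20 |
| Tube-fed | Both | 4/17 | 2/20 |
| Oral | Maintained oral | 16/17 | 17/17 |
| Oral | Both | 4/14 | 5/14 |

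Three checks confirm it:
- Either = oral + fall - both: 11+7-4 = 14 and 7+8-2 = 13.
- The printed tube-fed p-values reproduce: chi-square 0.107, 0.942 and 0.386; Fisher 0.383.
- Totals agree with Table 2. Score falls are 7+4 = 11 of 17+14 = 31, and 8+5 = 13 of 20+14 = 34. Oral feeders are 11+16 = 27 and 7+17 = 24. These equal the row "Feeding Outcome at Time 2" (27, 24), not "Feeding Method at Discharge" (29, 25), so Table 3 describes Time 2.

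**3. Stated rule at Time 2.** Tube-fed either + orally fed both: conventional 14+4 = 18; study 13+5 = 18.

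**4. Other pairings.** Taking each of oral feeding, fall, either or both for the tube-fed, combined with each for the orally fed, gives 16 pairings and eight distinct results (conventional/study): 27/24, 15/12, 23/25, 11/13, 30/30, 18/18, 20/19, 8/7. None is 16/13. The unsplit wording in Statistical Methods (oral feeding or score fall for everyone) gives 30/30.

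**5. Failure rule.** In the study arm all 20 tube-fed infants were scored and the 5 orally fed successes are among 14 scored, so the rule removes none of the 18. In the conventional arm one tube-fed infant has no score; at most one success goes, and only if that infant had reached full oral feeds. Reaching the printed counts therefore means failing 18-13 = 5 of 18 study successes (28%) and 1 or 2 of 18 conventional successes (18-16 = 2, less that one), all with complete Table 3 data. The four randomised infants absent from Table 3 (36-35 = 1; 40-37 = 3) cannot lower a success count. Switching infants between arms cannot help either, since the total is at least 35 against 29.

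**6. Discharge feeding with Time 2 scores.** Let k be the number of the 17 infants orally fed at inception who were on oral feeds at discharge, and D all oral feeders at discharge (29; 25). The minimum number of successes is max(tube-fed falls, D-k) + max(0, orally fed falls - (17-k)).
- At k = 17: conventional max(7, 12) + 4 = 16; study max(8, 8) + 5 = 13.
- Smaller k never lowers this. For example, conventional k = 13 gives 16+0, and study k = 12 gives 13+0.

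So 16 and 13 are attainable, but only at the floor; with k = 17 the ranges are 16-22 and 13-21. With k = 17, the study floor needs 5 of the 7 tube-fed infants on oral feeds at Time 2 to be off them at discharge, and all 6 score-only successes (8-2) to be on them.

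**7. A lead only.** Counting tube-fed infants solely by oral feeding at discharge, with k = 17, gives (29-17)+4 = 16 and (25-17)+5 = 13. That would drop the score alternative from the definition. If the one conventional infant off oral feeds at Time 2 was also off at discharge, it gives 13+4 = 17.

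**8. Effect on the estimate** (study minus conventional, Wald 95% CI, uncorrected chi-square; absent infants as failures).

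| Basis | Study | Conventional | Difference, points | p |
|---|---|---|---|---|
| Reported | 13/40 (32.5%) | 16/36 (44.4%) | -11.9 (-33.7 to +9.8) | 0.28 |
| Table 3 | 18/40 (45.0%) | 18/36 (50.0%) | -5.0 (-27.5 to +17.5) | 0.66 |
| Table 3, unscored infant failed | 18/40 (45.0%) | 17/36 (47.2%) | -2.2 (-24.7 to +20.2) | 0.85 |

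The third row applies only if the unscored conventional infant had reached full oral feeds. Exact intervals for the second row are 29.3-61.5 and 32.9-67.1.

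**The case against.** The strongest reply is that the two tables may describe different times. Outcome Measures places the endpoint at discharge when that precedes 5 weeks, and the median time from inception to discharge in Table 2 is 25 days, so at least half the infants left before day 35. If the headline uses discharge and Table 3 uses Time 2, the counts may differ without either being wrong, and step 6 shows that 16 and 13 are attainable that way. The floor there also relies on Time 2 scores. No discharge scores are tabulated, so the true floor could be lower.

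A second reply is that the Results refer to Figure 1 for the primary analysis and the drop-outs, and that figure was not available here. Sections 6.1 and 13.0 also let data collection continue after withdrawal, so some infants with complete data may have been classed as failures.

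These points stand as possible explanations and limit the finding: it does not show that 16 and 13 are wrong. They do not remove the discrepancy. Section 6.1 uses discharge only where Time 2 was not completed, the written failure rule does not cover scored infants, and no visible text says which time or rule was applied. The unchanged conclusion on superiority is conceded.

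**Conclusion.** The concern holds. At Time 2 the stated definition gives 18 and 18 successes from Table 3 against the reported 16 and 13, and no rule in the visible documents can be shown to produce the reported counts. Confidence is high for the mismatch; it does not extend to saying which table is in error.

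On Table 3 the study-arm deficit shrinks from 11.9 points to 5.0, or to 2.2 in the special case. The largest benefit not excluded rises from about 10 points to 17-20, still below the 27-point design target. These alternatives assume Time 2 assessment and failure for the four absent infants; if those infants could be successes, the counts become 18-19 conventional and 18-21 study. Because this is the primary estimate, the discrepancy must be resolved.

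**What to change.** Re-derive the primary endpoint from the locked infant-level data, using the Section 4.0 definition at the assessment time given in Section 6.1. Publish one cross-tabulation for all 76 infants: arm, feeding method at inception, oral feeding at assessment, and score fall (yes, no, missing), with the assessment time and the reason for each failure. Reconcile the timing in Outcome Measures and Section 6.1, the unsplit success wording in Statistical Methods, and Tables 2 and 3.

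- If 16 and 13 are an error, correct the counts, intervals and p-value in the Abstract, Results and Table 2.
- If Table 3 is wrong, correct Table 3.
- If 16 and 13 come from a different time point or failure rule, state that rule and report the Time 2 result beside it.

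The cost is one derivation re-run on locked data, one added table, and corrected or explanatory text. If timing is the explanation, a sentence and the extra result may suffice.
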